The original Greenlight Intervention. The initial efficacy trial of the Greenlight intervention was funded by NIH and applied evidence-based health literacy and health communication approaches to support clinician counseling and promote family engagement to prevent childhood obesity in children 2-24 months of age. The study successfully recruited and followed 865 English- and Spanish-speaking families and over 400 pediatric resident physicians in a cluster randomized trial. The study found improvements at 24 months at one site, but not the other, and this lack of improvement at 24 months was thought to be due to: 1) suboptimal engagement between 0-2 months (pre-intervention) and 18-24 months (no well child checks), and 2) lack of family support outside the clinical setting. The proposed study will evaluate the scalability/effectiveness of a more robust Greenlight program that includes additional clinical toolkit support starting at the first newborn visit and leverages technology to provide asynchronous support outside the clinical setting particularly at 18-24 months of life with children's changing feeding patterns. Prior studies across diverse populations have demonstrated the value of digital health platforms to improve patient/family behavior change.⁶⁵⁻⁶⁹

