Toolkit: Core Booklet and Tangible Tools: At each well-child visit, the physician presents the parent with a developmentally appropriate “Core Booklet,” and has the option to further reinforce messages with one of six Topic Supplements (breastfeeding, formula feeding, infant sleep, TV and other screen time, family physical activity, family nutrition). Each Core Booklet is tailored to the child’s developmental stage and corresponds to one of the routine well-child visits between birth and 18 months. To promote shared goal setting at each visit, the back page of each Core Booklet provides blank lines to allow for tailored goal-setting, as well as a check-box list to help guide families to make specific goals. Each Core Booklet introduces or reinforces three age-appropriate parent behaviors thought to be most strongly associated with preventing obesity during early childhood based on peer-reviewed literature.^{22,106,111,113,114,126,127,129,130}

Topics include: breastfeeding promotion, avoidance of sugary drinks, attention to satiety cues, promotion of healthy food choices, appropriate portion sizes, reduction in screen time, and activity promotion. Each of these behaviors is highlighted on the cover of each Core booklet within a green “traffic light”. We will review the booklets annually and update as needed to reflect any new guidelines that are published during the course of the study. At four of the well-child visits during study participation, the parent-child dyad will also receive a “Tangible Tool,” which is intended to promote intervention fidelity and reinforce Core Messages.

Revising the curriculum: Because this study will take several years to implement, it is possible that new evidence will become available that changes anticipatory guidance recommendations or best-practices for childhood obesity prevention. Each year the steering committee will evaluate the available literature to determine if updates to the training materials, intervention toolkit (i.e., booklets) or health information technology messaging is required. These changes will be documented in the study protocol.

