From the participant perspective, the experience using the intervention platform is simple. Parents take a short 10-minute survey asking about their behaviors and readiness for change (e.g., a parent of a 12- month-old would be asked: "How many ounces of juice do you usually give each day?" If more than 4 ounces per day, readiness and self-efficacy for reducing juice is assessed.) Based on responses, the system will immediately assign 1 personally-tailored behavior change goals for the care of their child (e.g., no juice, weaning from the bottle) to work on for 2 weeks. Every 2

weeks, participants will work on a new goal for novelty and to cover all domains associated with early life obesity prevention (e.g., sleep, eating, activity). Participants self-monitor their adherence to these goals via text messages sent 3 times per week. In these texts, participants also receive immediate tailored feedback based on their current adherence and long-term progress.

Based on self-monitoring data, we will send motivational messages to support participants' behavior change efforts. For each family, personalized "dashboards" will be maintained on the Greenlight website; parents will be able to easily access their dashboard using the link texted to them via the iOTA system or with their unique ID number. The dashboard will aggregate all activity on the platform site and content the participant has been texted via iOTA. Participants will be able to access Greenlight toolkit booklets and activities and track their child's goals and growth. Data from the iOTA platform will be pulled into each participant's dashboard by connecting directly to the iOTA platform. The participant dashboard will be built optimized for desktop, tablet, and smartphone display.

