11. STUDY DESIGN, STATISTICAL CONSIDERATION AND ANALYSIS PLAN

11.1 Analysis Plan

We will examine baseline characteristics of the two treatment arms using percentiles for continuous variables and percentages for categorical variables. The primary outcome is child weight for length (WFL) trajectory and secondary outcomes include: WFL Z-score, BMI Z-score, and the percent of children with overweight and/or obesity at 24 months. We will conduct *intent to treat* analyses that compare *the growth trajectories for children in the Greenlight Plus and Greenlight arms over the two years of follow-up*. We choose, as our primary outcome, WFL as opposed to Z-score or percentile because raw values have properties that are superior to standardized outcomes when conducting longitudinal growth modeling,¹⁴⁷ particularly when variables included in standardizations are included in regression models. Recent literature has highlighted problems with BMI-Z score (and other standardized BMI outcomes) for measuring extreme obesity (i.e., BMI percentiles >99%), especially in intervention contexts.¹⁴⁸ While the literature often reports Z-scores, we only include them as a secondary outcome because we believe their limitations outweigh their benefits. We chose WFL as opposed to BMI as our primary outcome since, for children age 0-2, the CDC recommends basing standards on WFL over BMI.

For primary and quantitative secondary outcome analyses, we will test the overall treatment effect (i.e., the combined treatment main effect and the treatment by age minus one month interaction) with a two-sided 0.05 significance level. To account for within-patient and within-site correlation, we will use linear mixed effects models.¹⁴⁹ From these models, we will estimate non-linear intervention effects across the age range (one through 24 months) using restricted cubic splines. Though the study will be randomized, eliminating the potential for confounding, we will control for baseline precision variables believed to be associated with outcomes, including, birth weight, gender, race and ethnicity, caregiver health literacy, caregiver's primary language, annual household income, food insecurity, and years of education. For the analysis of

overweight and/or obesity at 24 months, we will fit a longitudinal logistic regression model and summarize the results at the 24-month age to estimate and test for the intervention effect.

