model parameter estimates we generated child growth in simulated Arms of the study. We calibrated treatment effect sizes by assuming, due to randomization, outcome values between the two treatment arms were equal at study initiation, but children in the Greenlight Plus arm gain weight more slowly than in the Greenlight arm and in such a way that 24-month outcomes differ by a fraction of standard deviation in 24 month WFL. Let SD be the standard deviation in each outcome at month 24 (this is calculated based on original study estimates of the random intercept variance, random slope variance, and measurement error variance) and let ES be the effect size expressed as a fraction of SD. We generated and fit datasets 1000 times, conservatively assuming 30% attrition by the end of the study, to examine the power to detect differences in growth rates that induce a range of values for ES. We observed that we will have ample power for all outcomes if the ES is $\geq 0.2SD$ (the differences in trajectories lead to 0.2 SD differences in 24-month outcomes). The power to detect a treatment effect that is equal to 0.2SD is: 0.91 for WFL, 0.94 for WFL-Z, and 0.92 for BMI-Z. Because analyses of behavioral outcomes will involve binary (logistic), ordinal (proportional odds) and continuous (linear) data regression analyses, we focus on the power to detect treatment effects in the binary data setting due to their relatively low power. We assume 15% missing data for each analysis. We report power as a function of prevalence in the Greenlight arm (pG) and the odds ratios (OR) for the Greenlight Plus arm to the Greenlight arm. We calculate at least 80% power to detect a treatment effect (assuming equal sample size per arm): 1) for $pG=0.05$, $OR>2.20$, 2) for $pG=0.10$, $OR>1.83$, 3) for $pG=0.15$, $OR>1.69$, 4) for $pG=0.20$, $OR>1.61$, 5) for $pG=0.25$, $OR>1.56$, 6) for $pG=0.30$, $OR>1.53$, 7) for $pG=0.35$, $OR>1.51$.

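### Does the wording of the primary test leave the trial unable to see an effect that emerges after 18 months?

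*Combined protocol and SAP*

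**What the plan says.** Section 11.1 (Analysis Plan) specifies linear mixed models and tests "the overall treatment effect (i.e., the combined treatment main effect and the treatment by age minus one month interaction", "with a two-sided 0.05 significance level". The same rule covers the quantitative secondary outcomes. The paragraph goes on: from these models "we will estimate non-linear intervention effects across the age range (one through 24 months) using restricted cubic splines". The number and position of knots and the degrees of freedom are not given.

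The power text in Section 11.1 starts the two arms level and lets Arm 2 gain more slowly, so that they differ by a fraction of an SD at 24 months. Its stated purpose is "to examine the power to detect differences in growth rates that induce a range of values for ES". At 0.2 SD with 30% attrition it reports 0.91 for weight-for-length, 0.94 for its z-score and 0.92 for BMI z-score. It names the variance components but gives no values, and it does not name the test that was simulated.

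Section 3 attributes the earlier trial's lack of improvement at 24 months partly to "suboptimal engagement between 0-2 months (pre-intervention) and 18-24 months (no well child checks", and also to a lack of support outside the clinic. It says the new programme "leverages technology to provide asynchronous support outside the clinical setting particularly at 18-24 months of life". In Section 7.2 each Core Booklet "corresponds to one of the routine well-child visits between birth and 18 months". Under Arm 2, every two weeks "participants will work on a new goal for novelty and to cover all domains associated with early life obesity prevention", and the technology component begins at the newborn visit.

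**The concern.** The parenthesis names one interaction. Taken literally that is a 2-df test of a straight-line divergence, yet a model with a single linear treatment-by-age term cannot yield a non-linear intervention effect. A spline model has one interaction per spline term. The two sentences can therefore be read as two different primary tests.

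The choice would matter if the benefit came late. Booklets stop at 18 months in both arms while text-message goals continue in Arm 2, and Section 3 stresses 18 to 24 months. A difference that opens only then is sharply curved, and a straight line fits it poorly. At stake would be missing a real 0.2 SD difference at 24 months, and leaving the choice of primary test open until outcomes are known.

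**Working it through.** **1. The plan's own figure.** Power is the probability that a non-central chi-square with non-centrality λ exceeds its 0.95 critical value. Power of 0.91 at 2 df requires λ = 13.09. A linear effect lies inside the spline model, so λ stays the same and only the df rise: 0.91 (2 df), 0.873 (3 df, 3 knots), 0.840 (4 df), 0.809 (5 df). The 0.91 cannot be reproduced from first principles because the variance components are not reported.

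**2. Set-up for other shapes.**
- From the documents: 900 children (Section 1), 30% attrition, 0.2 SD at 24 months, and random intercept, random slope and error (Section 11.1).
- Assumed: 450 per arm; visits at 1, 2, 4, 6, 9, 12, 15, 18 and 24 months; retention falling linearly, 1 − 0.30 × (age − 1)/23.
- Formula: W = (450/2) × Σ p_m V_m⁻¹, where p_m is the proportion whose last visit is visit m and V_m is the covariance of visits 1 to m. Then λ = (X′Wd)′(X′WX)⁻¹(X′Wd), where d holds the true arm differences and X the treatment terms tested.

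**3. One worked split.** Take 24-month variance shares of 0.44 intercept, 0.36 slope and 0.20 error.
- Linear effect: λ = 12.99, power 0.91 at 2 df and 0.87 at 3 df. This is consistent with the plan's figure.
- Zero until 18 months, then rising to 0.2 SD: λ = 4.08, power 0.42 for the 2-df test. For 3 knots at 1, 9 and 18 months, λ = 12.57 and power is 0.86. With knots at 1, 12 and 24 months it is 0.92.

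**4. Range over assumed splits.** Intercept share 0.1 to 0.7 in steps of 0.1, error share 0.05 to 0.30 in steps of 0.05, slope the remainder. That leaves 41 splits with a positive slope share. A linear effect has 17/23 = 74% present by 18 months.

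| Share of the 0.2 SD present by 18 months | 2-df linear, median (range) | 3-knot joint, median (range) |
|---|---|---|
| None | 0.40 (0.28–0.70) | 0.91 (0.67–1.00) |
| A quarter | 0.59 (0.42–0.89) | 0.82 (0.56–1.00) |
| Half | 0.76 | 0.78 |
| 74% (linear) | 0.89 (0.75–1.00) | 0.85 (0.69–0.99) |

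The 0.91 in the first row is a median over assumed splits. It is not the plan's 0.91, which refers to a different effect shape. When the variances are tuned so that the 2-df test has exactly 0.91 for a linear effect, with error shares of 0.05 to 0.60, late-effect power is 0.30 to 0.50 (2 df) against 0.55 to 1.00 (3 knots).

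**5. Validity.** In 400 simulated trials per scenario with no effect, analysed by maximum likelihood under the plan's covariance, rejection was 0.045 (2 df) and 0.048 (3 df). Both hold 0.05.

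**6. Would prescribing a 3-knot test help?** Expected retention sums to 7.93 measurements per child, and the 24-month visit contributes 0.70, or 8.8%. A last knot at the 90th percentile of measurement age therefore falls at about 18 months. Fitted to the late shape, that model returns about 0.15 SD at 24 months (true value 0.20) and 0.07 SD at 18 months (true value 0). It detects a late effect but blurs its timing.

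**The case for a change.** The strongest case for a change is the asymmetry. The joint 3-knot test loses at most 0.06 if the effect is linear and gains 0.21 to 0.67 if it is wholly late. The two tests would disagree on significance in 0.4 to 9% of trials under a linear effect but in 23 to 67% under a late one. Section 10.1 unblinds the study statistician to outcome data, so an unstated knot count is real discretion. A sentence or two would settle it. There is also a poor literal reading, testing only the main effect and the first spline coefficient, with power of 0.26 to 0.91 (3 knots) for the linear effect.

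Part of this stands. The df and knots are not written down, the power text does not name its test, and a 2-df test is weak against a wholly late effect.

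The rest does not carry.
- **Which test is meant.** The non-linear effects come from the same models as the test, and what is tested is called the overall effect. In a spline model that means all treatment terms jointly. The weak readings fit the paragraph least.
- **How late the effect is.** Section 3 names 0 to 2 months as well as 18 to 24. The technology starts at the newborn visit and its goals rotate throughout. Both arms receive the same booklets. The power model diverges from study start. Zero effect to 18 months followed by 0.2 SD in six months is an extreme scenario brought to the plan from outside.
- **How much discretion remains.** On the joint reading only the knots are open. Three, four or five knots give 0.87, 0.84 or 0.81 under the plan's own alternative, all above 0.80.
- **What a stricter rule costs.** The joint test relies more on the covariance model. If 20% of the variance is serially correlated (an assumption), its model-based rejection rate with no effect is 0.092 against 0.062 for 2 df, and its late-effect power falls to 0.67.

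**Conclusion.** No change is called for. Section 11.1 fixes the joint null, the age origin, alpha, the model class and the covariates. What it omits is how many spline terms carry the interaction, and an analyst following the paragraph would test them all. If the linear test were run instead, it would still be valid at 0.05 and would have about 0.04 more power for the divergence the plan assumes. The large gap, about 0.40 (0.28 to 0.70) against about 0.55 to 1.00, appears only when the whole difference arises after 18 months. It rests on variance shares that the documents do not report, and it has closed by the point where half the effect is present at 18 months. Making a particular 3-df test compulsory would give up a little power under the plan's own alternative for protection against a shape the plan does not posit, and with the usual outer knot it would estimate that shape poorly. This is a gap filled sensibly in practice, together with a fair trade-off.

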We will also compare the participants in the current trial to an external cohort of children not enrolled in the current Greenlight Plus Study (GPS). At each site, the standard Greenlight (GL) Intervention will be administered to those randomized to it and to those who did not participate in the study. We will collect additional data that includes: 1) children who were not exposed to the present Greenlight Plus Study interventions because they were born in the years preceding GPS, and 2) children who were exposed to the Greenlight intervention because they received care during the GPS study time but were not enrolled in GPS.

Power calculations: We conducted simulation-based calculations to estimate the power for the primary outcome. We generated the Greenlight and Greenlight Plus data using linear mixed models of observed data in the original Greenlight study. From these

model parameter estimates we generated child growth in simulated Arms of the study. We calibrated treatment effect sizes by assuming, due to randomization, outcome values between the two treatment arms were equal at study initiation, but children in the Greenlight Plus arm gain weight more slowly than in the Greenlight arm and in such a way that 24-month outcomes differ by a fraction of standard deviation in 24 month WFL. Let SD be the standard deviation in each outcome at month 24 (this is calculated based on original study estimates of the random intercept variance, random slope variance, and measurement error variance) and let ES be the effect size expressed as a fraction of SD. We generated and fit datasets 1000 times, conservatively assuming 30% attrition by the end of the study, to examine the power to detect differences in growth rates that induce a range of values for ES. We observed that we will have ample power for all outcomes if the ES is $\geq 0.2SD$ (the differences in trajectories lead to 0.2 SD differences in 24-month outcomes). The power to detect a treatment effect that is equal to 0.2SD is: 0.91 for WFL, 0.94 for WFL-Z, and 0.92 for BMI-Z. Because analyses of behavioral outcomes will involve binary (logistic), ordinal (proportional odds) and continuous (linear) data regression analyses, we focus on the power to detect treatment effects in the binary data setting due to their relatively low power. We assume 15% missing data for each analysis. We report power as a function of prevalence in the Greenlight arm (pG) and the odds ratios (OR) for the Greenlight Plus arm to the Greenlight arm. We calculate at least 80% power to detect a treatment effect (assuming equal sample size per arm): 1) for $pG=0.05$, $OR>2.20$, 2) for $pG=0.10$, $OR>1.83$, 3) for $pG=0.15$, $OR>1.69$, 4) for $pG=0.20$, $OR>1.61$, 5) for $pG=0.25$, $OR>1.56$, 6) for $pG=0.30$, $OR>1.53$, 7) for $pG=0.35$, $OR>1.51$.

